8.7 Experimental Methods

After collection samples will be processed William Harvey Centre for Biochemical Pharmacology/Clinical Pharmacology Laboratories within one hour of following standard operating procedures listed in the *Lipid Mediator Unit Laboratory Manual*.

White Blood cell phagocytosis of Escherichia coli:

- 20 µl of blood will be incubated with 2×10^7 C.F.U. of fluorescently labeled E. coli

- Cells will be incubated at 37°C for 1h
- Cells will then be processed for flow cytometry using established protocols
- The extent of phagocytosis will be assessed using flow cytometry

Peripheral blood cell activation

- 20µl of whole blood will be incubated with or without 100µM of PAF for 1h at 37°C
- Cells will be washed 2x with PBS containing 5% fetal calf serum
- Cells will then be incubated with the following fluorescently conjugated antibodies for 15 min at room temperature
- Cells will then be processed for flow cytometry
- Adhesion molecule expression as well as platelet-leukocyte aggregates will be assessed using flow cytometry

Lipid mediator profiling

- Plasma (2ml) will be placed in 8 ml of ice-cold methanol containing deuterium labeled internal standards
- Samples will be stored at temperatures of -80°C
- Samples will be processed in batches of 20-24.
- Here samples will be centrifuged at 3000xg for 10 min at 4°C
- Supernatants will be collected
- Lipid mediators (LM) will be extracted using solid phase extraction techniques
- Isolated LM will be profiled using liquid chromatography tandem mass spectrometry (see ref 17)
- At the end of the study any excess or unused samples will be disposed of unless written consent is obtained from participant for longer term storage. Sample disposal will be conducted following standard operating procedures as outlined in the Biochemical Pharmacology laboratory manual.

RNA storage

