9.2 Secondary Endpoints

The secondary endpoints of this study are

- 1) an increase in *ex vivo* phagocytosis of *Escherichia coli* by peripheral white blood cells
- 2) a decrease in white blood cell activation when cells are incubated with an inflammatory stimulus (e.g. Platelet activation factor). This will be achieved by assessing the expression of adhesion molecules on peripheral blood cells using flow cytometry and fluorescently conjugated antibodies.

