9.3 Sample Size

Power calculations were conducted using data obtained from published studies where healthy volunteers were given 1 mg essentially (from a different source to that being investigated in the present study) and peripheral blood lipid mediator levels were evaluated pre-essential fatty acid and 4 hours after supplement intake (Colas et al Reference 17). Using pre and post values of 10 mediators values from these studies and Wilcoxon matched-pairs signed rank test a sample size of 33 participants is required to detect a threefold odds of an increase in post value when compared with the pre value with a power of 80% at the 5% level of statistical significance using the formulae from reference 18. Fifty mediators will be examined and it is recognized that at the 5% level of statistical significance around 2-3 mediators will falsely be identified as having significant changes. However the functional effect of all significant mediators will be subsequently examined by assessing white blood cell function, including the ability of peripheral white blood cells to phagocytose bacteria and the response of peripheral white blood cells and platelets to an inflammatory stimulus. If we do not observe increases in the ability of peripheral white blood cells to phagocytose bacteria and/or decreases in the activation of peripheral white blood cells and platelets then these mediators will be assumed to be false positive results. For these analysis the white blood cell function and peripheral blood lipid mediator levels at the 2h and 4h intervals post essential fatty acid/placebo administration will be compared to pre-supplementation values. The time point and dose that give the greatest change in all the mediators and the greatest regulation of peripheral white blood responses will be judged to be the main outcome measure for future trials.

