9.4 Statistical Analysis Plan

Wilcoxon matched-pairs signed rank test will be used to analyse the pre and post values of 10 mediators as well as white blood cell function (at 2 and 4h). The time point corresponding to the greatest number of the mediators being statistically significantly different from their pre-test values at the 5% level of statistical significance will be identified as the time point of interest. At the 5% level of significance testing 50 mediators will result in at least 2-3 associations being falsely statistically significant. Thus, the functional effect of all significant mediators will be subsequently examined by assessing white blood cell function, including the ability of peripheral white blood cells to phagocytose bacteria and the response of peripheral white blood cells and platelets to an inflammatory stimulus to determine if the identified associations are likely to be true changes. If we do not observe increases in the ability of peripheral white blood cells to phagocytose bacteria and/or decreases in the activation of peripheral white blood cells and platelets then these mediators will be assumed to be false positive results. Values at different times will not be compared just the value at each time point will be compared to the same person's pre test values.

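### The white-cell function rule in 9.3 and 9.4 is the only protection against false mediator findings, but it has no error control, 'and/or' can be read two ways, and a pass removes no false mediator

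*Combined protocol and SAP*

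**What the plan says.** Section 9.4 of the combined protocol and SAP states: "Wilcoxon matched-pairs signed rank test will be used to analyse the pre and post values of 10 mediators as well as white blood cell function", the latter at 2h and 4h. It expects 2-3 of 50 mediators to be falsely significant at 5% and gives no correction. Instead, white-cell function is examined "to determine if the identified associations are likely to be true changes". The decision rule begins "If we do not observe increases in the ability of peripheral white blood cells to phagocytose bacteria and/or decreases in the activation" of white cells and platelets; in that case the mediators are assumed to be false positives. Section 9.3 carries the same rule and says that function and mediator levels "at the 2h and 4h intervals post essential fatty acid/placebo administration will be compared to pre-supplementation values".

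The function endpoints in 9.2 are "an increase in *ex vivo* phagocytosis of" *E. coli* and a decrease in white-cell activation, measured by adhesion molecules. Section 8.7 adds: "Adhesion molecule expression as well as platelet-leukocyte aggregates will be assessed using flow cytometry". Section 8.3 gives every participant three active doses and placebo.

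The plan does not say which function readout decides, at which dose or time it must move, what counts as observing a change, or how error is shared across the function tests.

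**The concern.** Using function as a filter is the plan's substitute for a multiplicity correction of its primary analysis. Three features stop it from working as one.

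- **No error control.** The filter is itself a set of tests, and the only significance level in 9.4 is an unadjusted 5%.
- **Two readings of 'and/or'.** Suppose phagocytosis rises and activation does not fall. If mediators are dropped only when neither endpoint moves, all significant mediators are kept. If they are dropped when either fails to move, all are discarded. The choice could be made after the data are seen.
- **A group verdict.** No step ties a function result to a particular mediator. If function truly changes, for whatever reason, every falsely significant mediator is kept with the true ones.

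At stake is which mediators are reported as raised by fish oil, and the time point and dose that 9.3 would carry forward to later trials.

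**Working it through.** **Inputs.** From the documents: 50 mediators, 5% level, 80% power, threefold odds and 33 participants (9.3); 40 participants (synopsis, 8.3); times 2h and 4h (9.3, 9.4); three active doses (8.3); two function endpoints (9.2). Assumed: one readout per endpoint, function tested separately at each dose, two-sided tests counted in the favourable direction only (2.5% each), and common correlation ρ of 0, 0.5 or 0.8 between test statistics.

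**1. The plan's own figures.** False mediators: 50 × 0.05 = 2.5, matching the stated 2-3. This is for one set of 50 tests (one dose, one time) with no true changes. Sample size: threefold odds means p = 3/(1+3) = 0.75. Noether's signed-rank formula n = (z_α + z_β)² / [3(p − 0.5)²] gives (1.645 + 0.842)² / 0.1875 = 32.97, so 33, at one-sided 5%. At two-sided 5% it gives 41.9, so 42. The plan does not state sidedness.

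**2. Chance that the function rule passes with no true function effect.** The family is 2 readouts × 2 times × 3 doses = 12 tests.

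- Either endpoint suffices, ρ = 0: 1 − 0.975^12 = 26.2%.
- Both needed, ρ = 0: (1 − 0.975^6)² = 0.141² = 2.0%.
- For ρ > 0, let f(u) = Φ[(1.960 − √ρ·u)/√(1−ρ)]. Then P(either) = 1 − ∫f(u)^12 φ(u)du and P(both) = ∫[1 − f(u)^6]² φ(u)du.

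| Rule (12 tests) | ρ = 0 | ρ = 0.5 | ρ = 0.8 |
|---|---|---|---|
| Either endpoint suffices | 26% | 16% | 9% |
| Both needed | 2.0% | 4.8% | 4.6% |

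If function is read at one selected time (6 tests), the either-suffices figures are 14%, 10% and 7%. If tests are one-sided at 5%, as the match to 33 would allow, the 12-test figure at ρ = 0 is 1 − 0.95^12 = 46% for either and (1 − 0.95^6)² = 7.0% for both.

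**3. What a pass leaves behind.** All of the expected 2.5 false mediators per dose and time. If nothing is real and function is independent of the mediators, at least one of 50 is falsely significant with probability 1 − 0.95^50 = 92%. After the 12-test either-suffices rule, this is 0.262 × 0.923 = 24%. If function really changes, the rule passes and the 92% is not reduced.

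**4. Would matching dose and time be enough?** Under independence, one cell holds a false mediator increase with probability 1 − 0.975^50 = 71.8%, and a chance function pass with probability 1 − 0.975² = 4.9%. The product is 3.5%. Over six cells, 1 − (1 − 0.0355)^6 = 19%. With four readouts, 1 − 0.975^4 = 9.6%, and the six-cell figure is 35%. Matching helps but does not replace correcting the mediator tests.

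**5. Would correcting the function tests be a better route?** Holm over 12 tests starts at 0.05/12 = 0.0042. Exact two-sided sign-test power at p = 0.75 at that first step falls from 82% to 39% with 33 participants, and from 90% to 58% with 40.

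**The case against.** The strongest reply is that the synopsis calls the study exploratory with no formal statistical analysis, and that 9.3 uses the results to plan later trials. This stands as a reason for moderation, and no confirmatory claim should be read into the plan. It does not dispose of the point, because 9.3 and 9.4 still use 5% tests to declare findings true or false.

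A reader might infer that the rule passes by chance nearly half the time or more. The documents do not support that. Four readouts would give 24 tests and 1 − 0.975^24 = 46% under independence, and ten readouts 78%, but those counts are assumptions. Section 9.2 names two endpoints; aggregates appear only as an assay output in 8.7. The antibody list that 8.7 announces is absent from the text available here, and the laboratory manual it cites was not available, so the missing count should not be held firmly against the plan. With both endpoints required, the 12-test rate is not above 5% at any correlation tabulated.

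It can also be said that 9.4 selects one time point of interest and that 9.3 judges time and dose jointly on mediators and white-cell responses, which hints at linked reading. This lowers the figures but is nowhere stated as a rule. Finally, the rule does help when nothing is real (92% down to 24%). It gives no protection when function truly changes.

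**Conclusion.** The point holds as a defect in the rule itself. The lack of error control, the two readings of 'and/or' and the group verdict are in the text and need no simulation. The chance-pass rates (about 9-26% if either endpoint suffices, about 2-5% if both are needed) rest on one readout per endpoint, testing at every dose and both times, two-sided 5% and equal correlations. More readouts or one-sided tests raise them; a single time point lowers the either-suffices rate. It is not established that the rule often passes by chance, because that depends on a reading the documents do not settle.

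One uncertainty runs the other way. 9.4 compares each value only with the same person's pre-dose value, and 7.4 says diurnal variation in SPM is not known. Any time-of-day drift in white-cell function could open the filter more often than these figures show.

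**What to change.** Amend 9.3 and 9.4 as follows.

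1. State that function results are supportive and do not decide which mediators are true.
2. Control error on the mediator tests directly, for example with a false-discovery-rate procedure across the 50 mediators. State the family (50 per dose and time, or 50 × 6 = 300 overall) and reconcile 50 with the 10 mediators named in the test sentence of 9.4. Bonferroni at 0.05/50 = 0.001 is costly: the formula that gave 33 becomes (3.090 + 0.842)² / 0.1875 = 82.5, so 83.
3. Name one deciding phagocytosis readout and one deciding activation readout for the function statement; label the rest exploratory.
4. Replace 'and/or' by one stated rule.
5. Read function at the same dose and time as the mediator finding.
6. Acknowledge the exploratory status and reconcile the synopsis with 9.4.

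Holm across all 12 function tests is optional: it lowers power substantially and is not needed once the mediator tests are corrected.

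Cost: analysis wording only, with no new samples or assays. The downside is that fewer mediators will be declared changed.

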6.2 Original hypothesis

Given that fish oils are rich in omega-3 essential fatty acids that are precursors in the biosynthesis of SPM **the hypothesis underlying the present study is: Fish oil supplementation increase peripheral blood levels of SPM precursors that may**

be converted to bioactive mediators which in turn will regulate white blood cell responses.

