9. STATISTICAL CONSIDERATIONS

9.1 Primary Endpoint

The Primary endpoint of the study will be an increase in peripheral blood SPM levels that will be measured using established liquid chromatography tandem mass spectrometry based approach.

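### The rule that treats significant mediators as false positives when white-cell function does not change cannot tell real from chance hits, and lets a null secondary endpoint label a real primary result false

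*Combined protocol and SAP*

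**What the plan says.** - **Primary endpoint (6.3, 9.1):** "The Primary endpoint of the study will be an increase in peripheral blood SPM levels". No functional condition is attached.
- **Secondary endpoints (6.4, 9.2):** a rise in ex vivo phagocytosis of *E. coli*, and a fall in white-cell activation after an inflammatory stimulus.
- **Hypothesis (6.2):** function comes after the mediators. Precursors may "be converted to bioactive mediators which in turn will regulate white blood cell responses".
- **Testing (9.3, 9.4):** Wilcoxon matched-pairs tests against own baseline, at 2h and 4h, at the 5% level with no adjustment. The test "will be used to analyse the pre and post values of 10 mediators", yet the same section counts errors over 50: "At the 5% level of significance testing 50 mediators will result in at least 2-3 associations being falsely statistically significant". Section 9.3 puts it as "around 2-3 mediators will falsely be identified as having significant changes".
- **The rule (9.3, 9.4):** significant mediators are to be checked against white-cell function. Section 9.4 adds that this is to establish whether the associations are likely to be real. If phagocytosis does not increase "and/or decreases in the activation of peripheral white blood cells and platelets" are not seen, "then these mediators will be assumed to be false positive results".
- **Assays (8.7):** phagocytosis and activation are each read by flow cytometry on 20 µl of blood. No single mediator is added, blocked or isolated.
- **Use of the results (9.3):** "The time point and dose that give the greatest change in all the mediators" and the greatest change in cell responses sets the main outcome measure for future trials.

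**The concern.** The rule is the plan's only stated protection against chance findings among many mediators. To work, it would have to separate the few chance hits from the real ones. A functional readout belongs to a blood sample, not to a mediator, so it carries no information on which mediator in that sample truly rose.

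The rule also reverses the order of the endpoints. A measured rise in concentration is the primary endpoint, and a change in cell function is a later step in the hypothesis. If that step does not occur, or is missed, this does not show that the concentration rise was an error. The power calculation in 9.3 rests on mediator values only, so the tests that hold the veto have no stated power.

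At stake is the stated conclusion on the primary endpoint. A pattern of SPM raised with function unchanged would be described as a false-positive result, although it bears directly on the aim in 6.1.

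**Working it through.** **1. The plan's own figure.** Expected false positives if no mediator truly changes = 0.05 × number of tests. With 50 mediators tested once each, 0.05 × 50 = 2.5, which matches the plan's 2-3.

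**2. What the rule does to those hits.** Take the significant mediators judged against one functional result.

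| Functional result | Chance hits | Real rises |
|---|---|---|
| Changes | all kept | all kept |
| Does not change | all labelled false | all labelled false |

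In neither row are the chance hits separated from the real rises.

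**3. How often a real, detected rise is labelled false when function truly does not change.** The documents do not say what counts as observing a change, whether one or both readouts are needed, or whether the verdict is per dose and time or study-wide. I assume two independent readouts (phagocytosis and one activation measure) and no drift in function over the day. Where significance in the right direction is required, each null readout passes with probability 0.025, that is, one tail of a two-sided 5% test.

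| Reading of the rule | Formula | Labelled false |
|---|---|---|
| Significant, one cell, either readout suffices | 0.975² | 95.1% |
| Significant, one cell, both needed | 1 − 0.025² | 99.9% |
| Direction only, one cell, either suffices | 0.5² | 25% |
| Direction only, one cell, both needed | 1 − 0.5² | 75% |
| Significant, any pass at 2h or 4h suffices (2 × 2 = 4 tests) | 0.975⁴ | 90% |
| Significant, any pass in eight cells suffices (2 × 8 = 16 tests) | 0.975¹⁶ | 67% |

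Eight cells means three doses and placebo, each at 2h and 4h. Section 9.3 refers to values after active or placebo administration.

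**4. When function truly does change.** Power for function is not given, so I assume a range. At 80% power per readout, a real rise is still labelled false with probability 0.2² = 4% (either suffices) or 1 − 0.8² = 36% (both needed). At 50% power these are 25% and 75%. The unresolved and/or therefore matters in this case too.

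**5. The expected count over the tests that might be run.**

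| Tests | 50 mediators | 10 mediators |
|---|---|---|
| One per mediator | 2.5 | 0.5 |
| 2h and 4h, doses pooled | 5 | 1 |
| Three doses and placebo, each at 2h and 4h | 20 | 4 |

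These count changes in either direction if the tests are two-sided, which the plan does not state.

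**6. The words at least in 9.4.** An expected value is not a minimum. With 50 independent null tests, the chance of 0 or 1 false hits is 28% (binomial, n = 50, p = 0.05).

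**The case against.** **The study is exploratory.** The synopsis (section 4) says so and says there will be no formal statistical analysis. This lowers the stakes. It does not remove a rule that 9.3 and 9.4 both state, and no other section limits it.

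**The headline percentages depend on a criterion the rule does not state.** This stands. Section 9.4 applies the Wilcoxon test to white-cell function, so significance is the likelier reading, but the rule speaks only of what is observed. One verdict per dose and time is also an interpretation. Because function is compared with own baseline, drift over the day could make the check pass without any supplement effect. Section 7.4 says diurnal variation in SPM is unknown; drift in function would be a further assumption. The figures are conditional for these reasons.

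**A reader might infer that a rise in SPM with unchanged function could not be reported at all.** The documents do not support that. The synopsis says results will be tabulated, and section 20 commits relevant data to publication. The rule governs the label and the conclusion, not the release of data.

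**Reference to the functional effect of significant mediators might suggest mediator-level testing.** Section 8.7 describes no such assay.

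**Removing the rule removes the only guard.** True, but it is a guard that cannot discriminate. Function can still be reported as supportive evidence. The and/or wording, unnamed activation readouts, unstated sidedness and 10-versus-50 discrepancy are mainly missing detail or wording. They widen the range in the working but do not carry the point.

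**Conclusion.** The point holds. As written, the rule gives one verdict to all mediators judged against the same functional result, so it cannot pick out the expected chance hits. It also lets a null result on a secondary endpoint of unstated power label a real rise in the primary endpoint false. That follows from the text of 8.7, 9.1, 9.3 and 9.4 and needs no numerical assumption.

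The size does need assumptions. With function truly unchanged and two independent readouts, a real detected rise is labelled false about 95% to 99.9% of the time under the significance reading in one cell. It is 25% to 75% if only direction counts, and about 90% to 67% if any significant pass across two to eight cells suffices. No single figure in that range can be presented as the plan's error rate, because the plan does not define the rule closely enough.

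**What to change.** 1. In both 9.3 and 9.4, delete the sentence that assumes mediators are false positives when function does not change. In 9.4, also delete the statement that function will determine whether the associations are true changes.
2. Report mediator results on the primary endpoint in their own right, labelled as unadjusted.
3. Beside them, state the expected number of false positives as 0.05 × the number of tests actually run (2.5, 5 or up to 20 for 50 mediators, as above), and drop the words at least.
4. Reconcile 10 with 50 mediators so that this count is defined.
5. Report phagocytosis and activation as secondary endpoints and as supportive evidence only.

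**Cost:** wording only, with no added sampling and no loss of sensitivity for the mediators. The downside is that when nothing truly changes, chance hits that the rule would often have discarded are shown. They would carry the unadjusted label and the expected count. The change does not settle how 9.3 chooses the dose and time point for future trials; that text remains as it is.
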